5.3.4. Primary Endpoint Analysis

The primary endpoint of this study is the proportion of participants who achieved an ACR 20 response at Week 24. This section outlines the definitions and analyses of this primary endpoint.

5.3.4.1. Definition of Endpoint

ACR response is a composite measurement of change in PsA signs and symptoms and is presented as the numerical measurement of improvement in multiple disease assessment criteria (Felson 1993, 1995). An ACR20 response is defined as:

1. ≥20% improvement from baseline in both tender joint count (68 joints) [TJC68] and swollen joint count (66 joints) [SJC66]

AND

- 2. \geq 20% improvement from baseline in at least 3 of the following 5 assessments:
 - a. Patient's Assessment of Pain (Visual analog scale [VAS]) [PAIN]
 - b. Patient's Global Assessment of Disease Activity (arthritis, VAS) [GDPT]
 - c. Physician's Global Assessment of Disease Activity (VAS) [GDEV]
 - d. Patient's Assessment of Physical Function as measured by HAQ-DI
 - e. C-reactive protein (CRP)

Following are the definitions of each of the forgoing disease assessment criteria (components) that are used in the determination of ACR20 response:

- 1. Tender Joint Count 68 (TJC68): a total number of tender joints among the 68 joints evaluated for tenderness. Each of the 68 joints will be evaluated for tenderness, categorized as tender or not tender. Joint evaluability rules specified in Section 6.10 for overwriting joint evaluation will be applied to those joints with joint injection(s)/surgical joint procedure(s). For participants with any joint not evaluable in the 68 joint set, joint count adjustment rules described in Section 6.10 will be applied in determining the ultimate count of tender joints.
- 2. Swollen Joint Count 66 (SJC66): a total number of swollen joints among the 66 joints evaluated for swelling. (Note: The 2 hip joints are excluded from swelling assessment.) Each of the 66 joints will be evaluated for swelling, categorized as swollen or not swollen. Joint evaluability rules specified in Section 6.10 for overwriting joint evaluation will be applied to those joints with joint injection(s)/surgical joint procedure(s). For participants with any joint not evaluable in the 66 joint set, joint count adjustment rules described in Section 6.10 will be applied in determining the ultimate count of swollen joints.
- 3. Patient's Assessment of Pain (PAIN): a measure from 0 (no pain) to 10 (the worst possible pain) on a 10-unit VAS.

- 4. Patient's Global Assessment of Disease Activity (arthritis, GDPT): a measure from 0 (very well) to 10 (very poor) on a 10-unit VAS.
- 5. Physician's Global Assessment of Disease Activity (GDEV): a measure from 0 (no arthritis activity) to 10 (extremely active arthritis) on a 10-unit VAS.
- 6. HAQ-DI: a measure of difficulty a participant may have in accomplishing tasks in 8 functional areas. For additional details, please refer to the definition of HAQ-DI in Section 5.3.6.2.2.
- 7. C-reactive protein (CRP): a lab parameter measured in mg/dL. Lower limit of quantification (LLOQ) rule specified in Section 6.10 will be applied to values <LLOQ.

If a participant's baseline value for a component is zero (ie, no disease activity as measured by that component), the participant should be considered as not achieving 20% improvement from baseline for that component since there is no room for improvement.

Additional supplementary analyses will be conducted on the primary endpoint using Treatment Policy Estimand, aiming to achieve a robust treatment effect for regulatory decision making.

5.3.4.2.2. Treatment Policy Estimand (Supplementary)

The treatment policy strategy is to use all observed data collected for the endpoint. The occurrence of the intercurrent event (ICE) is irrelevant: the value for the variable of interest is used regardless of whether or not the ICE occurs. This is the supplementary strategy aiming to achieve a robust treatment effect for regulatory decision making for primary and some major secondary endpoints.

This estimand is defined by the 5 components:

- **Population**: same as Adjusted Composite Estimand
- Treatment: same as Adjusted Composite Estimand
- Variable: ACR20 composite binary response variable at Week 24, where a responder is defined as a participant who achieves ACR20 response at Week 24 irrespective of background PsA medication or adherence to study intervention
- **Intercurrent Events**: the definitions of the 5 categories of ICE are same as the Adjusted Composite Estimand
- **Population level summary**: difference in proportion of responders (as per definition of **Variable** above) between guselkumab group and placebo group

This estimand examines the difference in proportion of participants who achieve ACR20 response after 24 weeks irrespective of background PsA medication or adherence to study intervention, between each guselkumab group individually versus placebo, amongst participants with active PsA who had an IR and/or intolerance to one prior anti-TNF.

5.3.4.3. Analysis Methods

The primary efficacy analysis of the primary endpoint will be analyzed at Week-24 DBL based on the **Adjusted Composite Estimand**.

In the primary efficacy analysis, data from all participants in FAS (Section 4.2) will be analyzed according to randomized intervention group regardless of the treatment actually received.

ICE Strategies

For the Adjusted Composite Estimand, ICEs 1-3 are incorporated as part of the endpoint using the composite strategy. This estimand acknowledges that a participant increasing their background PsA medications or electing to discontinue study intervention for reasons other than Natural Disaster or Major Disruption prior to the assessment timepoint is an unfavorable outcome, and thus for the purpose of analysis they are considered treatment failures (TF) and set to ACR20 non-responders at Week 24.

This estimand also possesses a hypothetical component, regarding significant unplanned changes to study conduct as a result of Natural Disaster or Major Disruption. This estimand seeks to estimate the treatment effect of study intervention as if the above, as well as ICEs directly resulting from it, did not occur. Thus, data observed after the occurrence of ICEs 4 and 5 will not be used and will be considered MAR and imputed using FCS MI on the individual ACR components.

Should there be a participant who meets ICEs from both the composite strategy and the hypothetical strategy, the composite strategy has precedence, and they will be set to an ACR20 non-responder at Week 24.

Handling Rules for Missing Data

After ICE strategies have been implemented, remaining missing data will be handled as follows:

- 1. **Missing Week 24 ACR 20 response due to Natural Disaster or Major Disruption**, will be assumed to be MAR and imputed using FCS MI on the individual ACR components.
- 2. Missing Week 24 ACR 20 response NOT due to Natural Disaster or Major Disruption, will be considered MAR but imputed conservatively as an ACR 20 non-responder (NRI rule) at Week 24 to be consistent with historical studies.

Analysis Testing

The treatment difference between each guselkumab group versus the placebo group will be tested using a CMH test stratified by baseline use of non-biologic DMARDs (yes, no) for each imputation set, and the Wilson-Hilferty (Ratitch 2013) transformation will be applied to the CMH statistics across the imputation sets. The transformed CMH statistics will be combined to calculate the p-values according to Rubin (Rubin 1987). The magnitude of the treatment difference will be estimated by the difference in ACR 20 response rates between the guselkumab and placebo groups with a 95% CI calculated based on Wald statistics (Kim 2013).

In order to control the overall Type 1 error rate, the primary endpoint will be tested in a fixed sequence.

- 1. Guselkumab 100 mg q4w versus placebo in ACR 20 response at Week 24, among FAS participants
- 2. Guselkumab 100 mg at Weeks 0, 4, and then q8w versus placebo in ACR 20 response at Week 24, among FAS participants

If the first test is significant at a 2-sided α -level of 0.05, the study will be considered positive, and the second test can then be performed.

5.3.4.4. Sensitivity and Supplementary Analyses

- 1. (Sensitivity Analysis 1) To evaluate the robustness of the Adjusted Composite Estimand regarding the assumptions for missing or not used data, sensitivity analyses with the exhaustive two-dimensional scenario tipping point analyses will be performed. The analysis will be conducted for an 'exhaustive approach' testing all combinations of missing data imputation as responder and non-responder (NR) (Section 5.3.2.2). Note that data imputed as part of the ICE strategy (ie, NR due to meeting ICEs 1-3, FCS MI due to meeting ICEs 4 and 5) will be performed prior to the tipping point analysis. The chi-square test will be used to compare each guselkumab group versus the placebo group. This will avoid the complication of having to incorporate baseline stratification in the mix when generating all combinations of responders and NR for the missing data for CMH test. As all combinations will be presented, both the points where tipping occur, as well as the proportion of non-tipping combinations, are of interest.
- 2. (Sensitivity Analysis2) To assess the effect of excluding all Ukrainian participants from the analysis for the Adjusted Composite Estimand, as all sites in Ukraine have been impacted by Major Disruption (eg, study intervention interruptions, temporary site closures, etc) to a larger or smaller extent. The same analysis of ACR 20 response at Week 24 as the primary analysis will be performed on the FAS-UKR analysis set.
- 3. (Sensitivity Analysis 3) To assess the effect of protocol deviations which may affect efficacy, a sensitivity analysis similar to the main analysis will be performed but based on the PPAS.
- 4. (Sensitivity Analysis 4) As the Major Disruption has the potential to prevent source data verification (SDV) from taking place (eg, due to site closure, site inaccessibility, etc), an analysis will be conducted to assess the impact by excluding affected participants. The same analysis as the main analysis will be performed on the FAS analysis set, excluding participants for which the expected SDV was not completed for data on or prior to Week 24.
- 5. (Supplementary Analysis 1) To support regulatory decision making, the Treatment Policy Estimand (Section 5.3.4.2) will also be evaluated as a supplementary analysis. In this analysis, the observed ACR 20 response for all participants will be used regardless of whether or not ICE criteria are met prior to Week 24, and the missing ACR 20 response will be imputed by FCS MI (Section 5.3.2.1) on the component level under the assumption that data are MAR. Treatment comparisons for each imputation data set will be based on a CMH test stratified by baseline use of non-biologic DMARDs (yes, no), as per Section 5.3.1. This analysis will be conducted based on the FAS-UKR analysis set.
- 6. (Supplementary Analysis 2) An additional tipping point analysis for the Treatment Policy Estimand will be performed. The observed ACR 20 response for participants will be used regardless of whether or not ICE criteria are met prior to Week 24, and the missing ACR 20 response will be imputed by FCS MI (Section 5.3.2.1) on the component level under the assumption that data are MAR. In this analysis, a pair of deltas will be added to the predicted response rates from MI method depending on guselkumab or placebo group to new MI datasets (Section 5.3.2) to evaluate deviation from the assumption of MAR for missing data. The same analysis method as in the primary analysis will be applied for the pairs of deltas. The analysis will be done for pairs of delta values include the scenarios where participants on

guselkumab have worse outcomes than participants on placebo. This analysis will be conducted based on the FAS-UKR analysis set.

Subgroup Analyses

Subgroup analyses will be performed using the Adjusted Composite Estimand using a logistic regression model on the multiply imputed data to evaluate treatment consistency in proportion of participants who achieve an ACR 20 response at Week 24 over baseline demographics, baseline disease characteristics, and prior and baseline medication use. A forest plot will be produced for all subgroups listed in Section 5.5.5. The odds ratios and the corresponding 95% CIs will also be provided for each of the subgroups (Section 5.3.1). In addition, the p-values for interaction of the intervention groups and the subgroups will also be provided when a subgroup has at least 2 categories.

If the number of participants in a subgroup is too small (eg, <10), subgroups may be pooled for analyses.

5.3.4.5. Summary of Analyses Related to the Primary Endpoint of ACR 20 Response at Week 24

Table 6 below provides an overview on all the analyses related to the primary endpoint of ACR 20 response at Week 24, the estimands, the data handling rules to be used, and the analysis methods and summary statistics. Section 5.3.2 provides a summary of the MI method.

Table 6: Summary of Analyses Related to the Primary Endpoint of ACR 20 Response at Week 24

Analysis (Estimand) – Analysis Set	TF/Missing data imputation	Additional notes
Primary Analysis (based on Adjusted Composite Estimand) – FAS	ICEs 1-3 considered as TF ICEs 4 and 5, data not used, but rather imputed using FCS MI Missing data due to Natural Disaster or Major Disruption assumed MAR, imputed via FCS MI Missing data not due to Natural Disaster or Major Disruption assumed MAR but conservatively imputed as non-response	 Summarized descriptively Pooled response rates, treatment difference in response rates and 95% CI across multiply imputed data sets P-value from CMH statistic with Wilson-Hilferty transformation across multiply imputed data sets
Sensitivity Analysis 1 (based on Adjusted Composite Estimand) – FAS	ICEs 1-3 considered as TF ICEs 4 and 5, data not used, but rather imputed using FCS MI, then averaged across MI datasets. Missing data rules not applied. Response rate of missing data varied with all possible combinations of response status for missing data. Single imputation	 Exhaustive 2-dimensional tipping point analysis; graphical The chi-squared test is used to compare intervention groups, for each coordinate on the graph separately

Analysis (Estimand) – Analysis Set	TF/Missing data imputation	Additional notes
Sensitivity Analysis 2 (based on Adjusted Composite Estimand) – FAS-UKR	ICEs 1-3 considered as TF ICEs 4 and 5, data not used, but rather imputed using FCS MI Missing data due to Natural Disaster or Major Disruption assumed MAR, imputed via FCS MI Missing data not due to Natural Disaster or Major Disruption assumed MAR but conservatively imputed as non-response	 Summarized descriptively Pooled response rates, treatment difference in response rates and 95% CI across multiply imputed data sets P-value from CMH statistic with Wilson-Hilferty transformation across multiply imputed data sets
Sensitivity Analysis 3 (based on Adjusted Composite Estimand) – PPAS	ICEs 1-3 considered as TF ICEs 4 and 5, data not used, but rather imputed using FCS MI Missing data due to Natural Disaster or Major Disruption assumed MAR, imputed via FCS MI Missing data not due to Natural Disaster or Major Disruption assumed MAR but conservatively imputed as non-response	 Summarized descriptively Pooled response rates, treatment difference in response rates and 95% CI across multiply imputed data sets P-value from CMH statistic with Wilson-Hilferty transformation across multiply imputed data sets
Sensitivity Analysis 4 (based on Adjusted Composite Estimand) – FAS, Excluding Participants with Non-SDV'd Data Through Week 24	ICEs 1-3 considered as TF ICEs 4 and 5, data not used, but rather imputed using FCS MI Missing data due to Natural Disaster or Major Disruption assumed MAR, imputed via FCS MI Missing data not due to Natural Disaster or Major Disruption assumed MAR but conservatively imputed as non-response	Summarized descriptively Pooled response rates, treatment difference in response rates and 95% CI across multiply imputed data sets P-value from CMH statistic with Wilson-Hilferty transformation across multiply imputed data sets
Supplementary Analysis 1 (based on Treatment Policy Estimand) – FAS-UKR	No ICEs considered as TF Missing data assumed MAR, imputed via FCS MI	 Summarized descriptively Pooled response rates, treatment difference in response rates and 95% CI across multiply imputed data sets P-value from CMH statistic with Wilson-Hilferty transformation across multiply imputed data sets

Analysis (Estimand) – Analysis Set	TF/Missing data imputation	Additional notes
Supplementary Analysis 2 (based on Treatment Policy Estimand) – FAS-UKR	No ICEs considered as TF Missing data imputed via FCS MI, then imputed data response rate varied and generated using Bernoulli distribution	 2-dimensional tipping point analysis to assess robustness of analysis results should there be deviation from MAR assumption of missing data; graphical P-value from CMH statistic with Wilson-Hilferty transformation across multiply imputed data sets, for each coordinate on the graph separately
Subgroup Analyses (based on Adjusted Composite Estimand) – FAS subgroups	ICEs 1-3 considered as TF ICEs 4 and 5, data not used, but rather imputed using FCS MI Missing data due to Natural Disaster or Major Disruption assumed MAR, imputed via FCS MI Missing data not due to Natural Disaster or Major Disruption assumed MAR but conservatively imputed as non-response	 Odds ratio and 95% CI for treatment comparison P-value from logistic regression for the interaction of intervention group and subgroup variable Graphical: forest plots

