5.3. Efficacy Analyses

5.3.1. General Method of Analysis

In general, descriptive statistics, such as mean, standard deviation (SD), median, interquartile (IQ) range, minimum, and maximum for continuous variables, and counts and percentages for discrete variables will be used to summarize most data.

Statistical comparison between a guselkumab group (100mg q4w or 100mg at Weeks 0, 4 and then q8w) and the placebo group will be performed by visit through Week 24. No treatment comparisons will be performed after Week 24.

Binary Response Efficacy Endpoints

For binary response efficacy endpoints where any portion of the missing data is imputed using Multiple Imputation (MI) (see Section 6.12 for technical details), treatment comparisons will be performed using a Cochran-Mantel-Haenszel (CMH) stratified by baseline use of non-biologic DMARDs (yes, no) on each of the imputation sets, and the inferences from the analysis of each imputed data are pooled. The within imputation variance and between imputation variance are combined to estimate the total variance of the stratum adjusted difference of proportions. This estimate of the variance and critical values from the t-distribution are used to calculate the confidence interval for the stratum adjusted difference of proportions. The SAS procedure PROC MIANALYZE is used where the critical value is based on the t-distribution which is different from the analysis not based on MI where normal distribution is used. The large number of observations in our data imply that the critical values from the t-distribution are almost identical to the critical values from the standard normal distribution. The Wilson-Hilferty (Ratitch 2013) transformation is used to pool the CMH statistics from each imputed data set to calculate the p-value.

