5.3.2.2. Imputing Missing Data Evaluating Deviation from Assumptions (Tipping Point Analyses)

5.3.2.2.1. For Primary Endpoint

For the **Primary endpoint** (ACR 20 response at Week 24) using the Adjusted Composite Estimand (see Section 5.3.4.2 for definition of estimand), the exhaustive scenario tipping point analyses will be performed to evaluate any deviation from the imputation of: missing NOT due to Natural Disaster or Major Disruption (see Section 5.3.4.2) being imputed as non-responder, and missing due to Natural Disaster or Major Disruption being imputed using FCS MI under MAR assumptions.

Note that as part of the ICE strategies for the Adjusted Composite Estimand (see Section 5.3.4.2), participants who meet ICEs 1-3 prior to Week 24 are set to non-responder regardless of observed data, and participants who meet ICEs 4 or 5 prior to Week 24 are imputed using FCS MI regardless of observed data. These participants, combined with participants with observed data at Week 24 who did not meet any ICEs prior that timepoint, comprise the not-to-be-varied group for the Adjusted Composite Estimand, and their response rate remains static through the tipping point analysis.

Let T_A be the total number of imputed values to-be-varied in the Active arm, where i of them will be set to 'Yes' response and (T_A-i) of them set to 'No' response. In the same vein, let T_P be the total number of imputed values to-be-varied in the Placebo arm, where j of them will be set to 'Yes' response and (T_P-j) of them set to 'No' response. The range of i is from 0 to T_A , and a range of j is from 0 to T_P , which is an 'exhaustive approach'.

Also for the **Primary endpoints** but using the Treatment Policy Estimand (see Section 5.3.4.2 for definition of estimand), the tipping point analyses based on imputed data by FCS MI will be performed to evaluate the impact of imputed when deviating from the MAR assumption.

- A pair of deltas (eg, Dg =-0.1, Dp =0.2) will be added to the predicted response rates of each missing data from the MI method depending on guselkumab or placebo group.
- With the new response rate, the missing response will be imputed for N (eg, N=200) times to generate N multiple imputations based on a Bernoulli distribution. Treatment comparisons will then be performed same as treatment comparison with MI.
- The range of delta values includes the scenarios where participants on guselkumab have worse outcomes than participants on placebo.

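### Sensitivity Analysis 1 averages the imputed ICE 4/5 responses before a single chi-square test, so its p-values leave out between-imputation variance and are generally too small near 0.05 where such participants exist

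*SAP*

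**What the plan says.** ICE 4 is stopping injections because of a natural disaster or major disruption. ICE 5 is severe non-compliance for the same reason, which for the primary endpoint means at least two missed doses (SAP 5.3.4.2.1).

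For binary endpoints with any multiply imputed data, SAP 5.3.1 tests each imputed data set and pools the results: "The within imputation variance and between imputation variance are combined to estimate the total variance". The p-value comes from Wilson-Hilferty pooling of the CMH statistics. Appendix 12 sets 200 imputations.

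Sensitivity Analysis 1 is described in three places.

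- SAP 5.3.2.2.1: "participants who meet ICEs 4 or 5 prior to Week 24 are imputed using FCS MI regardless of observed data". They belong to the group that is not varied, and "their response rate remains static through the tipping point analysis".
- SAP 5.3.4.4, item 1: "The chi-square test will be used to compare each guselkumab group versus the placebo group". The reason given is to avoid handling the stratification factor. Imputation variance is not mentioned.
- SAP 5.3.4.5, Table 6, for ICEs 4 and 5: "data not used, but rather imputed using FCS MI, then averaged across MI datasets". The row is labelled as single imputation, and "The chi-squared test is used to compare intervention groups, for each coordinate on the graph separately". No pooling step is named.

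The other tipping-point analysis of this endpoint, Supplementary Analysis 2 in the same table, does pool: "P-value from CMH statistic with Wilson-Hilferty transformation across multiply imputed data sets, for each coordinate on the graph separately".

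**The concern.** Averaging 200 imputations and then testing once on the full sample treats participants whose data were set aside as if they had been observed. The spread between imputations, which measures what is not known about them, never reaches the test. This is a question of the standard error, separate from which participants the grid varies.

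The analysis has some weight. Protocol 9.4.2 names the exhaustive tipping-point analysis as the robustness check on the primary endpoint, and it is the only tipping-point analysis of the primary estimand; Supplementary Analysis 2 uses the treatment policy estimand and excludes Ukraine. SAP 5.3.4.4 says the grid will be read by where tipping occurs and by the proportion of non-tipping combinations. Both depend on where p crosses 0.05. The analysis runs on the full analysis set, which keeps the Ukrainian sites, where SAP 4.3 reports supply interruptions and temporary closures.

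**Working it through.** **Inputs.** 150 per arm, 2-sided 0.05, and ACR 20 rates of 22.2% / 52.0% / 59.4% (PSA3001) and 19.8% / 44.4% (PSA3003), all from SAP 3.1; 200 imputations (Appendix 12). The ICE 4/5 count is not stated, so a range is assumed.

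**The plan's own figure.** The SAP gives no number for this analysis. Its power statement reproduces with a two-proportion test: 99.98% (22.2 v 52.0), above 99.99% (22.2 v 59.4) and 99.65% (19.8 v 44.4). At 70% of the effect it is 97.4%, 99.8% and 91.5%.

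**Upper bound on the standard error.** Let a fraction f of each arm have ICE 4/5. With no predictive auxiliary data, the average of many imputations tends to the arm's observed rate. The estimated rate then has variance p(1-p)/[n(1-f)], while the chi-square test uses p(1-p)/n. So

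SE used / true SE = sqrt(1-f), and the real p at a displayed 0.05 is 2 x [1 - Phi(1.96 x sqrt(1-f))].

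| f | SE ratio | SE understated by | Real p at displayed 0.05 |
|---|---|---|---|
| 2% | 0.990 | 1% | 0.052 |
| 5% | 0.975 | 3% | 0.056 |
| 10% | 0.949 | 5% | 0.063 |
| 20% | 0.894 | 11% | 0.08 |

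**Check by simulation.** Take k ICE 4/5 participants per arm of 150, with beta-binomial imputation standing in for FCS. Adding the between-imputation variance, W + (1+1/M)B, multiplies the SE by 1.010, 1.027, 1.054 and 1.117 at k = 3, 8, 15 and 30. The inverses (0.990, 0.974, 0.949, 0.895) agree with the table. With no ICE 4/5 participants the factor is 1.

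**Near the 0.05 line (about 32.5% v 22%).**

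| k per arm | p, averaged | p, Rubin | p, Wilson-Hilferty |
|---|---|---|---|
| 3 | 0.0341 | 0.0346 | 0.0339 |
| 8 | 0.0398 | 0.0441 | 0.0432 |
| 15 | 0.0442 | 0.0547 | 0.0535 |
| 30 | 0.0354 | 0.0573 | 0.0561 |

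**Effect on the grid.** The number of varied participants is also assumed.

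- 52.0% or 59.4% v 22.2%, with 10 or 20 varied per arm: every cell stays significant under all methods.
- 44.4% v 19.8%, 10 varied per arm: the same.
- 44.4% v 19.8%, 20 varied per arm: the non-tipping share stays at 96.6% for k = 3 and 8. It goes from 96.6% to 95.2% (Rubin) or 95.9% (Wilson-Hilferty) at k = 15, and from 96.1% to 93.7% at k = 30.
- 70% of the PSA3003 effect (0.7 x 24.6 = 17.2 points, so about 37.0% v 19.8%), 20 varied per arm, averaged to Wilson-Hilferty: no loss at k = 3; 76.9% to 75.7% at k = 8; 77.3% to 75.1% at k = 15; 75.1% to 70.3% at k = 30.

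**The case against.** A reader might infer more than the documents support.

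- **That every p-value on the grid is too small.** It is not. A comparison without ICE 4/5 participants is unaffected. Wilson-Hilferty pooling, the SAP's own method, can give a smaller p than averaging: 0.0339 against 0.0341 in the k = 3 row above, and 0.782 against 0.987 at 22% v 22% with k = 15. In the latter case the averaged difference is near zero, but the individual data sets scatter around it and each yields a positive statistic. With k = 3 and 20 varied per arm (44.4% v 19.8%), averaging gave the smaller p in 92.7% of cells.
- **That the trial's result will look more robust than it is.** This depends on a count the documents do not give. SAP 4.2 and 4.3 say only that no site lost every participant and that Ukrainian sites were potentially affected, so nothing supports 10% or 20% per arm as likely. The imputation model uses the seven ACR components from Week 0 to Week 24, so data before the event would usually shrink the effect.
- **That this explains why the grid need not reproduce the primary p-value.** The grid also uses an unstratified test and varies disruption-related missing data that the primary analysis imputes. Pooling removes neither difference. Dropping stratification can even raise p: 0.0382 against 0.0378 for CMH, and 0.0367 against 0.0330 with a stronger stratum effect.
- **That each participant enters as a known fractional count.** This is a reasonable reading of the averaging and single-imputation wording, but the SAP does not say how a non-integer average enters a chi-square test.

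It is also fair to say that the grid is graphical, lies outside the testing hierarchy and has no pass/fail rule, and that Sensitivity Analysis 2 drops Ukraine with full pooling. These points limit the consequences. They do not supply the missing variance. Nor does the SAP 5.3.1 provision for singly imputed data help, because it applies only where all missing data are imputed once.

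**Conclusion.** The point holds as a standard error that is wrong as specified: this row departs from the SAP's own rule, and the only reason given for the chi-square test concerns stratification. Where ICE 4/5 participants exist, p-values near 0.05 are generally too small. The understatement of the SE runs from about 1% to 11% as the affected share goes from 2% to 20% of each arm. Those figures assume equal shares in both arms and no predictive auxiliary data, so they are an upper bound. At the planning effects the loss of non-tipping cells is nil up to about 8 per arm and about 2.4 points (96.1% to 93.7%) at 30 per arm. It is larger with a smaller effect, up to 4.8 points (75.1% to 70.3%) in the cases run. The primary analysis itself is not affected.

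**What to change.** In Table 6, delete the clause on averaging across imputed data sets and the single-imputation label. At each (i, j) coordinate, run the chi-square test in each of the 200 data sets imputed for ICE 4/5 and pool with the Wilson-Hilferty/Rubin step already used in the primary analysis and in Supplementary Analysis 2. The unstratified test can stay, so the SAP's practical reason for it is respected. The question of non-integer counts then disappears. Report the number of ICE 4/5 participants per arm beside the grid, so that a reader can see how much the imputation contributes.

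The cost is a wording change and some computing time. The share of non-tipping combinations may fall slightly.
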